2.1. Objectives, Endpoints, and Estimands

Objectives	Endpoints
Efficacy	
To compare the efficacy of intraocular implants containing travoprost at two different elution rates versus Timolol Maleate Ophthalmic Solution, USP, 0.5% (Timolol) in reducing elevated intraocular pressure in subjects with open-angle glaucoma (OAG) or ocular hypertension (OHT).	Primary Efficacy Endpoint: • Change from baseline in IOP in the study eye at 8AM and 10AM at each of Day 10, Week 6, and Month 3 visits (6 timepoints).

Estimand: the four attributes of the estimand are defined as the following:

- 1. Population: ITT population including all randomized subjects. Subjects with open-angle glaucoma or ocular hypertension defined through enrollment criteria.
- 2. Variable (endpoint): Change from baseline in IOP at 8AM and 10AM at each of Day 10, Week 6, and Month 3 visits (6 timepoints).
- 3. Intercurrent events: the following categories are potential intercurrent events for this study, which could be related to study treatment and require an adjustment to the imputation strategy for the efficacy analyses:

2.2. Study Design

This is a prospective, randomized, double-masked (subject and observer), active-controlled, parallel-group, multicenter trial comparing the efficacy and safety of the Model G2-TR-063 Travoprost Intraocular Implant and the Model G2-TR-125 Travoprost Intraocular Implant to topical Timolol in subjects with OAG or OHT. A total of approximately 558 males and females \geq 18 years of age who were diagnosed with OAG or OHT will be randomized to one of three treatment arms in a 1:1:1 allocation:

- G2-TR-063: Travoprost Intraocular Implant, high elution rate (Model G2-TR-063), with placebo eye drops.
- G2-TR-125: Travoprost Intraocular Implant, low elution rate (Model G2-TR-125), with placebo eye drops..
- Concurrent Control: Sham surgery with Timolol Maleate Ophthalmic Solution, USP, 0.5% (timolol).

The randomization will be stratified into two groups based on baseline mean diurnal IOP

Subjects are required to meet all eligibility criteria at the Screening visit. If the subject is using ocular hypotensive medications at this visit, she/he is required to complete the appropriate medication washout period listed below before returning for the Baseline visit; subjects who are not using hypotensive medication may be scheduled for a Baseline visit (on a separate day).

is

in the study eye after medication washout period.

Following completion of the baseline visit, eligible subjects are scheduled for the operative examination. At this visit, subjects will be randomized to treatment and per randomized assignment, either implanted with G2-TR-063, G2-TR-125, or have the sham surgical procedure performed.

Follow-up visits are scheduled at postoperative Day 1-2, Day 10, Weeks 4, 6, Month 3 and every 3 months thereafter through Month 36.

Postoperatively, for the duration of the study, subjects in the G2-TR-063 and G2-TR-125 arms are instructed to use placebo eye drops (artificial tears) twice daily in the study eye, while subjects in the control arm, following sham surgery, are instructed to instill topical timolol 0.5% eye drops, solution twice daily in the study eye. The investigator could administer or prescribe ocular hypotensive medication at a first or later after the operative exam based on the IOP values, please refer to the Figure 3 in the protocol for post-treatment management of IOP and rescue medications.

The pre-specified primary efficacy endpoint is IOP at each of the six timepoints through 3 months postoperative (8:00 AM and 10:00 AM at Day 10, Week 6, and Month 3).

Safety parameters included adverse events, best spectacle corrected visual acuity, slit lamp biomicroscopy findings, gonioscopy findings, specular microscopy findings (at selected sites), ophthalmoscopy findings (including cup-to-disc ratio), and visual field evaluation.

2.3. Assessment Schedule

2.4. Sample Size Determination

In order to detect adverse events that occur at a rate of 1% or higher, safety in the clinical program will be demonstrated in a minimum of 300 subjects who have completed the expected duration of drug elution from either implant model.

3. Analysis Sets

Intent to Treat Analysis Set (ITT)

This analysis set includes all subjects who are randomized.

Per-Protocol Analysis Set (PP)

The Per-Protocol analysis set is a subset of the ITT analysis set. It includes all the ITT subjects who received the study treatment based on the randomization schedule and do not have major protocol deviations likely to impact the primary efficacy endpoints.

Safety Analysis Set

The safety analysis set will contain all subjects who are randomized and receive at least one dose of study treatment. Subjects will be grouped according to their actual treatment received,

4. General Statistical Considerations

Continuous data will be summarized with the number of non-missing values, mean, standard deviation, minimum, median, and maximum. Other selected percentiles, such as the 25th percentile and 75th percentile may be presented for parameters that are not normally distributed or are suspected of exhibiting that tendency. Categorical data will be summarized with the number of non-missing values and the numbers of values equal to each of the possible values. Percentages of subjects with each of the possible values will be calculated from the number of subjects in the relevant cohort of the corresponding analysis set, unless stated otherwise. Some continuous variables may also be grouped into categorical levels and evaluated in frequency tables.

All inferential statistical analyses will be performed with a two-sided confidence level of 95% or a two-sided significance level of 0.05, except when stated otherwise using SAS[®] software, Version 9.4, or higher.

Data displays produced for this study will include three types: summary tables, data listings, and figures.

Data listings will simply list the data recorded on the case report form (CRF) or derived for each subject. They will be ordered by treatment, subject number, study eye, and time of assessment. Additional levels of ordering may be employed as appropriate. Data listings will not display subject initials.

In general, summary tables will be presented by treatment group:

- Implant
- Implant
- Sham/Timolol

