6.1.8. Subgroup Analyses

Subgroup analyses will be performed for the primary efficacy endpoint in the ITT analysis set with the . The subgroups are defined as follows:

- Age (<65 vs. \geq 65)
- Sex (Male vs. Female)
- Race (White vs. Non-White)
- Type of disease (OAG vs. OHT)
- Baseline mean diurnal IOP

The primary efficacy endpoint will be summarized separately for each subgroup to evaluate

	-
.   2	

		2
	Į	

7. Safety Analyses

The safety analyses will be based on the safety analysis set.

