7.1.5. Gonioscopy and Implant Visibility Assessment

Gonioscopy will be used to assess angle abnormalities including presence of goniosynechiae, angle anatomy and implant location (in eyes with implants) for both the study eye and fellow eye at Screening, Day 10, Weeks 4, 6, and Months 3, 6, 12, 18, 24, 30, and 36. The Shaffer angle grade will be collected only at screening visit for eligibility criteria.

The number and percentage of subjects in each category will be summarized for the study eye.

Gonioscopy findings include abnormal anatomy, goniosynechiae, rubeosis, and other angle abnormalities. The number and percentage of subjects with the gonioscopy findings at each scheduled visit will be summarized by treatment group for the study eye.

The implant visibility assessment will be performed during gonioscopy examination. The number and percentage of subjects with implant location not in original position, or implant being anchored but migrated at any visit will be summarized by treatment group.

Gonioscopy and implant visibility assessment will be presented in data listings.

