7.1.6. Ophthalmoscopy

Ophthalmoscopy will be performed with pupil dilation to examine the fundus and nerve abnormalities for the study eye at Screening, Months 3, 6, 9, 12, 15, 18, 21, 24, 27, 30, 33, and 36. The dilated fundus exam will include evaluation of the macula and vessels as well as peripheral fundus examination.

In addition, the number and percentage of subjects with any clinically significant findings at any post-baseline visits, and at each scheduled post-baseline visit will be also presented by treatment group.

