7.1.10. Specular Microscopy

Specular microscopy will be only captured at selected sites. Specular microscopic central image will be taken in the study eye at Screening, Month 3, Months 12, 24 and 36. Endothelial cell density, percent hexagonality, and the coefficient of variation (COV) will be assessed from calibrated specular microscope images. At each examination, average endothelial cell density for each eye will be reported by the reading center and used for analysis.

The actual, change from baseline, and percent change from baseline in central endothelial cell density will be calculated for each post-baseline visit and summarized by treatment group.

In addition, the number and percentage of subjects with \geq 30% loss from baseline in central endothelial cell density will be summarized by treatment group for study eye as overall (i.e., based on the minimum change from baseline across any post-baseline visits), and by visit.

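### Does the undefined percentage base in SAP section 4 understate the rate of ≥30% endothelial cell loss, which is measured only at selected sites?

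*SAP*

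**What the plan says.** SAP section 4 sets two general rules for categorical tables, one after the other. The first fixes what is counted: "Categorical data will be summarized with the number of non-missing values and the numbers of values equal to each of the possible values". The second fixes the base of percentages, which "will be calculated from the number of subjects in the relevant cohort of the corresponding analysis set, unless stated otherwise". The same section adds: "In general, summary tables will be presented by treatment group".

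For safety, SAP section 7 states: "The safety analyses will be based on the safety analysis set". Section 3 defines that set as the randomized subjects who received study treatment. It defines no subset of subjects with specular images.

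SAP section 7.1.10 opens with the restriction "Specular microscopy will be only captured at selected sites". It ends by asking that the number and percentage of subjects with at least 30% "loss from baseline in central endothelial cell density will be summarized by treatment group", both overall and by visit. It names no denominator, so the section 4 default applies.

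Protocol section 9.4 rules out imputation for safety outcomes, rests safety summaries on the data available in the safety population, and lists endothelial cell count among the descriptive summaries, noting there that it comes from selected sites. SAP section 1 says the SAP takes precedence over the protocol on definitions and methods, and that the table shells are a separate document.

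**The concern.** Section 4 names the non-missing count and then, in the next sentence on categorical data, uses a different and undefined phrase for the percentage base. Because tables are by treatment group and safety analyses use the whole safety set, a programmer could take the cohort to be the full arm. Subjects at sites without a specular microscope could then never be counted as events but would still sit in the denominator, even with perfect follow-up.

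The outcome matters. Specular microscopy is a key safety measure in the protocol synopsis, the product is an intraocular implant, and follow-up runs to 36 months. Safety outcomes are not formally tested, so the descriptive percentages carry the message.

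The same wording governs other by-visit findings, such as "The number and percentage of subjects with the gonioscopy findings at each scheduled visit will be summarized by treatment group" (SAP section 7.1.5) and "the number and percentage of subjects with any clinically significant findings at any post-baseline visits" (SAP section 7.1.6). On a full-arm base those percentages would shrink as visits are missed.

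**Working it through.** **Inputs**
- Arm size: 558 / 3 = 186, as in the protocol synopsis.
- Share of the arm imaged, *f*: not given. Assumed values are 0.75, 0.50 and 0.25, that is about 140, 93 and 46 subjects.
- Rate of ≥30% loss among imaged subjects, *p*: not given. Assumed values are 5% and 10%.

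The plan states no endothelial-loss rate and no number imaged, so there is no figure to reproduce on this point.

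**Arithmetic if the base is the full arm**

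Events = *f* × 186 × *p*. Printed rate = (*f* × 186 × *p*) / 186 = *f* × *p*. On the imaged base the printed rate is *p*.

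| Share imaged | Subjects imaged | Printed when *p* = 5% | Printed when *p* = 10% |
|---|---|---|---|
| 0.75 | 140 | 3.8% | 7.5% |
| 0.50 | 93 | 2.5% | 5.0% |
| 0.25 | 46 | 1.2% | 2.5% |

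In whole subjects, 5/93 = 5.4% but 5/186 = 2.7%. A difference of 10% against 2% is 8 points among those imaged and 8 × 0.50 = 4 points on the full arm at *f* = 0.50. With the same *f* in both arms the ratio is unchanged: 10/2 = 5 and 5/1 = 5.

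**Does the text require that base?**
1. *Choice of word.* Where the SAP describes how a table is laid out, it says treatment group, in section 4 and again in 7.1.10. The percentage rule uses another word, qualified as relevant and placed inside an analysis set. That describes a subset suited to the table at hand at least as well as it describes the arm. For specular microscopy the evident subset is the subjects at the imaging sites, because 7.1.10 begins by restricting capture to them.
2. *Protocol.* Section 9.4 points to the subjects with data. It does not name a percentage base, so it does not settle the matter alone, but it favours the imaged reading.
3. *Precedence.* The SAP's priority clause operates where the SAP defines something differently. An undefined phrase is not a contrary definition, so the two documents can be read together.
4. *Visibility.* The non-missing count is required for categorical tables and also for the continuous summaries of cell density in 7.1.10. A table showing 5 cases and 93 non-missing values gives the reader 5/93 = 5.4%, whichever percentage is printed.
5. *Unseen text.* The default yields wherever another base is stated. Denominators and footnotes normally appear in table shells, which are not among the documents.

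**Other by-visit findings.** On a full-arm base, a 10% rate among those assessed prints as 10% × 0.9 = 9%, 10% × 0.8 = 8% or 10% × 0.7 = 7% when 10%, 20% or 30% (assumed) are not assessed. That is modest. Treated-set and assessed-only bases are both used for such tables, and the assessed-only base can itself be biased if missing visits are informative. For the overall specular row, attrition does not simply multiply in: it uses the extreme change over all post-baseline visits, so a subject imaged at Month 3 who leaves later still contributes.

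**The case for a change.** The strongest case for a change is that the author had the non-missing count to hand and chose a different phrase. With no imaged subset defined and safety tables by arm, the full arm is a permissible reading. Two programmers could then print rates that differ two-fold at a 50% imaged share or four-fold at 25%. The direction does not depend on the assumed share, since any share below 100% lowers the rate. A reader can recompute, but the printed percentage is the one that gets quoted, and one sentence would remove the doubt.

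The ambiguity stands, and so does the arithmetic. What does not stand is the step from an undefined phrase to a misreported rate. Nothing visible directs that subjects who were never imaged be counted, and the protocol's rule on available data leans the other way. A full-arm base would also leave a visible mismatch between the non-missing count and the percentage in the same table. An argument about confidence intervals that are too narrow has no object here, because 7.1.10 plans only a number and a percentage.

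**Conclusion.** No change to the plan follows. The SAP leaves a term undefined, and analysts working from the protocol's available-data rule, with the non-missing count in the table, would very probably use the imaged subjects as the base. If they did not, the printed rate would fall by the share not imaged: 25%, 50% or 75% at assumed imaged shares of 0.75, 0.50 and 0.25. The true share is not in the documents. The ratio between arms would be preserved provided the imaged share is similar across arms, which is also an assumption. Efficacy is untouched, and no safety test or planned interval depends on this percentage. For gonioscopy and ophthalmoscopy the choice of base is largely one of convention. The conclusion would be different only if the table shells fixed the full arm as the base for the specular microscopy table, and nothing in the documents indicates that.

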4.1. Definition of Variables

4.1.1. Baseline

Baseline for analysis purposes is defined as the last assessment prior to treatment start date/time.

4.1.2. Change and Percent Change from Baseline

• Change from baseline is defined as the post baseline value minus the baseline value.

For standard IOP, the post-baseline collection time will be mapped in order to calculate the change from baseline value.

• Percent change from baseline is calculated as follows: Percent change = (Change from baseline / Baseline) * 100.

4.1.3. Study Days

Study day for analysis purposes is defined as (date of event – surgery date) (+1 if the event occurs on or after surgery start date).

Study Day 1 is the date of surgery. Study Day relative to date of surgery will appear in the listings where applicable.

4.2. Analysis Windows

Data at each scheduled follow up visit will be analyzed according to the nominal visit identified on the data record. The order of nominal visits will be consistent with chronological order of the study visit date. All assessments including scheduled and unscheduled will be presented in the data listings.

4.3. Adjustment for Covariates

4.4. Handling Missing Data

4.4.1. Handling of Missing Data/Intercurrent Events for Efficacy Variables

Please see section 6.1.3 for handling missing IOP data/intercurrent events for the primary analysis.

4.4.2. Imputation of Incomplete Medication/AE Dates

For analyses of adverse events (AEs) and concomitant medication usage, a complete date must be established in order to correctly identify the AE or medication as occurring during treatment or not. For purposes of imputing missing components of partially reported start and stop dates for AEs and for medication use, the algorithms listed below will be followed. Start and stop dates of AEs or concomitant medication will be displayed as reported in the subject data listings (i.e., no imputed values will be displayed in data listings).

Partial AE and concomitant medication start/stop dates will be imputed as follows:

4.5. Multiple Study Centers

4.6. Handling Rescue Medication

Post-treatment rescue medications will be captured in the Concomitant Medication eCRF for the study eye. Two strategies will be applied to account for rescue medication separately:

5. Demographic and Baseline Characteristic Analyses

5.1. Subject Disposition

Reasons for screen-failure (including baseline-failure, i.e., subjects enrolled but not randomized) will be tabulated.

Exit status will be classified as completed or discontinued (including reason for discontinuation) for each randomized subject. The reasons for premature discontinuation are:

Exit status at Months 3, 12, and 36 will be summarized as number and percent by treatment group and overall for the ITT analysis set.

The number of subjects who were randomized and the number of subjects within each analysis set (ITT, Safety, and PP) will be summarized by treatment group.

Subject disposition data will be provided in a listing. A separate listing describing each subject's inclusion or exclusion status for each of the analysis sets will also be provided.

5.2. Protocol Deviations

Protocol deviations will be captured by the site and reviewed by the medical monitor during the study. Classification between major or minor deviations will be decided by the study team prior to database lock. Subjects with major protocol deviations will be excluded from PP analysis set.

All protocol deviations will be listed and summarized by type and treatment group for the ITT analysis set.

5.3. Demographic and Baseline Characteristics

Demographic and baseline subject characteristics will be summarized for the ITT analysis set. Demographics will include age, sex with child-bearing potential for females, race, and ethnicity.

The baseline clinical characteristics include the following variables:

- Type of disease (OAG or OHT) in the study eye
- Baseline Study Eye IOP
- Baseline best spectacle corrected visual acuity in study eye LogMAR
- Iris Color for study eye

- Visual Field Mean Deviation (dB) for study eye
- Vertical Cup-to-Disc Ratio for study eye
- Corneal Thickness (µm) for study eye

A listing of demographic and baseline information will be provided.

5.4. Medical History

Medical history including ocular and non-ocular medical history will be collected in the eCRF. The Medical Dictionary for Regulatory Activities will be used to code all medical history terms to a System Organ Class (SOC) and Preferred Term (PT). Ocular and non-ocular medical history will be summarized for the ITT analysis set separately by SOC in alphabetical order, preferred term in alphabetical order, and by treatment group. Subjects reporting more than one PT within a SOC will be counted only once for that SOC.

Ocular and non-ocular medical history will be presented in listings.

5.5. Prior and Concomitant Medications/Procedures

Prior and Concomitant Medications

Prior medication is defined as any medication taken prior to the date of the surgery. Concomitant medication is defined as any medication taken on or after the surgery date. If any medication is taken before the surgery date and continues after the surgery date, it will be considered as both a prior and concomitant medication.

Prior/concomitant medications will be coded to therapeutic class and preferred term using the World Health Organization Drug Dictionary

The number and percentage of subjects who had taken prior/concomitant medications will be summarized for the ITT analysis set by therapeutic class and preferred term, and by treatment group. Subjects taking the same medication multiple times will only be counted once for that therapeutic class and preferred term. A subject level listing will also be presented.

Concurrent Ocular Procedures

Concurrent ocular procedure is defined as any ocular procedures performed for the study eye after the surgery date. Concurrent ocular procedures will be provided in a listing.

Non-study IOP Lowering Medications

A non-study IOP-lowering medication is defined as an IOP-lowering medication taken for the study eye other than that to which the subject was randomized.

The number and percentage of subjects

will be summarized for the ITT analysis set by type of disease (OAG vs. OHT) and treatment group.

A listing of the prior and concomitant non-study IOP-lowering medications for study eye will be provided.

5.6. Intercurrent Events

Intercurrent events include the following categories:

6. Efficacy Analyses

6.1. Primary Efficacy Endpoints Analysis

6.1.1. Definition of Endpoints

The primary efficacy measure in this study is the change from baseline in IOP. Diurnal IOP is evaluated at Baseline Day 10 Week 6 Months 3

	is evaluated at Dasenne, Day 10, week 0, Wonth's 5,
12 and 24. Standard IOP	is evaluated at Week 4, Months
6, 9, 15, 18, 21, 27, 30, 33, and 36.	

The primary efficacy endpoint is the change from baseline in diurnal IOP in the study eye at 8AM and 10AM at each of Day 10, Week 6, and Month 3 visits (6 timepoints).

